## **5.2 Recruitment Methods**

This is non-interventional study that does not require contact with study subjects. All subjects will be identified from the Mayo Clinic CP Registry, the VA Pathology & Laboratory Medicine Service, and from the VA CDW.

## **5.3 Informed Consent Procedures**

There will not be any contact with subjects in the study and study subjects will not be consented into the study. We are requesting an Exemption Category 4.iii for secondary research use of identifiable private information or identifiable biospecimens.

## **5.4 Inclusion/Exclusion Criteria**

The population to study will include all Veterans who have tested positive for SARS-CoV-2 and treated for COVID-19 within the VHA healthcare system. Data available in the VA CDW will be utilized. Data analyses will assess multiple domains at the inpatient and outpatient level and obtained through the central VA COVID-19 Shared Data Resource. Domains for Data Analysis will include, but not limited to, Initial Presentation, Prior Medical Diagnoses, Health Limitations and Habits, Current Medications, Hospital Admission and Lab, Hospital Course, and Post Discharge Course. Data review will begin from date of diagnosis, short- and long-term outcomes will be assessed up to 1-year following diagnosis. There are no exclusion criteria for this study.

## **5.5 Study Evaluations**

This is non-interventional, retrospective data study, and therefore we will be using VA CDW data within the VA healthcare system.

## **5.6 Data Analysis**

### **Data Collection/Study Measures**

Data will be identified and captured using CPRS, on VHA servers and the CDW using the VINCI servers. Data captured will come from several VHA healthcare data sources and National Patient Care Databases (NPCDs), including: VA Pathology & Laboratory Medicine Service,

Veterans Health Information Systems and Technology Architecture (VistA) Medical SAS Outpatient Clinic and Patient Treatment File (PTF) datasets, Vital status crosswalk File with Real SSNs, Vital Status File with Scrambled SSNs, the Decision Support System (DSS) National Data Extract (NDE), Beneficiary Identification Records Locator (BIRLS) death file, Pharmacy files, and Pharmacy Benefit Management (PBM) system database. Data contain information on clinic visits, inpatient hospitalizations within VA, diagnosis, and procedure codes. Pharmacy data and laboratory data are available as well. All electronic databases related to the study will be stored on double password protected servers behind the VA firewall. Data accessed remotely via VINCI or in CDW will be accessible only by approved study personnel using strong IDs and passwords.

As needed, data from VINCI/CDW will be reviewed by study staff and entered into a VA REDCap database. Each Veteran identified will be assigned a unique study ID. A crosswalk document will be kept within VINCI that will link the study ID to the Patient ICN. This document will be the only document to link study data and will be kept secure within on the study's VINCI workspace and will only be accessible to a limited number of study staff conducting data review. The variables below represent a desirable list of information that will be captured using REDCap. We recognize that some of the information will not be available. Where feasible, we will make imputation for some information items.

Analyses conducted on the study will receive internal quality control checks by an approved data analyst that was not involved in the data analysis. Below we describe the primary data and variables we will use to accomplish the aims of the proposal. The list of data and variables is not exhaustive but provides a detailed summary of the types of data will be using.

### **Exposure: CP Treatment**

The primary exposure of interest is the use or the non-use of CP. These data are derived from multiple sources, including the VA Pathology and Laboratory Medicine Service, CDW, and the Mayo Clinic CP Registry. Data on CP recipients from the Mayo Clinic and VA Pathology and Laboratory Medicine Service will be matched to EHR data with unique identifiers, which include name, date of birth, VA patient identifiers (e.g., Patient ICN), date of hospitalization, and VA medical center or hospital. Other identifying information to match records may also be available, such as Social Security Numbers from the VA Pathology and Laboratory Medicine Service. Mayo Clinic data will not include Social Security numbers.

### **Outcome variables**

The primary outcome is 30-day all-cause mortality.

### **Other Covariates of Interest**

**Initial Presentation:** date of encounter, date of birth, sex, race, ethnicity, zip code of residence, date symptoms started.

**Prior Medical Diagnoses:** chronic obstructive pulmonary disease, coronary heart disease, cardiac failure, diabetes mellitus, hypertension, cerebrovascular disease, chronic liver disease, cancer of solid organ, estimated glomerular filtration rate, immunodeficiency, autoimmune disorder [RA, IBD, lupus, etc.]

**Health Limitations and Habits:** smoking (never, former, current).

**Current medications:** diabetes oral medication, diabetes insulin used, immunosuppression therapy, blood pressure therapy, angiotensin converting enzyme angiotensin converting enzyme

(ACE) inhibitors, angiotensin-receptor blockers (ARBs), beta blockers, human immunodeficiency virus therapy.

**Outpatient Management Course:** including symptoms at home, VA physician management, “progression of symptoms” and re-evaluation at the medical center, viral lab testing, and short- and long-term outcomes.

**Hospital Admission and Lab:** VA Facility, admission date, Initial Admission to (ward, isolation, ICU, ICU on ventilator, other), chest x-ray lung findings at admission, PaO2, admission and hospital course laboratory extremes (white blood cell count, lymphocyte count, platelet count, hemoglobin, CRP, procalcitonin, serum sodium, serum potassium, serum chloride), and admission and hospital abnormal values (lactate dehydrogenase (LDH), aspartate transaminase (AST), alanine aminotransaminase (ALT), bilirubin total, creatine kinase (CK), dDimer), influenza vaccine in EHR over past 12 months, assay used to diagnose SARS-CoV-2 infection, and co-infection with other respiratory viruses.

**Hospital Course:** ICU (start date and end date) complications (sepsis, acute kidney injury, rhabdomyolysis, ARDS, disseminated intravascular coagulation, pneumonia diagnosed by MD, hours to pneumonia from admission, hospital treatment (IV antibiotics, IV antifungal, IV antiviral (+name of antiviral), kidney dialysis, glucocorticoids, extra corporeal membrane oxygenation, IV immunoglobulin, IV hyperimmunoglobulin), other COVID-19 treatments, hospital discharge (date) and discharge facility or outcome (residence, nursing facility, death)

**Post Discharge:** COVID-19 antibody assay results and titer if available. Post discharge general medicine, cardiovascular care, and infectious disease follow up notes to estimate ability to perform activities of daily living. Use of VA medical care facilities and diagnoses in the recovery phase of the epidemic with focus on chronic disease complications with abstraction of information in outpatient encounters and communications with VA providers.

### **Statistical Analysis Plan**

The target trial to emulate would include US Veterans hospitalized at a VA medical center where CP was a current practice. The patient would become eligible at the first SARS-CoV-2-positive test date (if the positive test occurred during hospitalization) or at the hospital admission date (if the positive test occurred before hospitalization).

Eligible patients would be randomly assigned to either receive or not receive CP. The exact timing of transfusion and determination of suitability for use (based on antibody levels or donor characteristics of the plasma units) would be left to the discretion of treating physicians. The primary outcome would be 30-day mortality. The causal contrasts of interest are the intention-to-treat effect and the per-protocol effect. To estimate the intention-to-treat effect (the effect of assignment to CP on outcomes), estimate the risk difference and hazard ratio comparing patients in the CP and non-CP group. The risk (cumulative incidence) of outcomes could be estimated nonparametrically using the Kaplan-Meier method or under parametric smoothing assumptions via a pooled logistic regression model including a time-varying intercept, an indicator for treatment group, and a product (“interaction”) term between time and treatment group. The hazard ratio could be estimated from the pooled logistic regression model without the product term. In the case of a prespecified imbalance in baseline characteristics between intervention arms, relevant covariates could be added to the model.

To estimate the per-protocol effect (the effect of treatment with CP on outcomes if all patients had adhered to the protocol), we would restrict the above intention-to-treat analysis to patients who adhered to their assigned treatment (CP or no CP) and adjust for the a priori baseline prognostic factors, as well as trial start day relative to first eligibility. The adjustment for these covariates would be carried out via inverse probability weighting, with all continuous variables

flexibly modeled using restricted cubic splines and estimated weights truncated at the 99.9th percentile to prevent extreme weights from affecting the analyses. In a secondary analysis, the adjustment for these covariates will instead be carried out via standardization. In all analyses, we use nonparametric bootstrapping, which yields unbiased estimates of standard error, to calculate percentile-based confidence intervals (CI) for survival difference and hazard ratio estimates.

Combined analysis with other cohorts in the Mayo Clinic CP Registry: Other health systems in the registry will be performing similarly data analyses. Research groups are encouraged to share the same data analysis plan. Some will contribute summary statistics to a research collaboration.

### **Sample Size/Power**

We present power calculations here for the mortality outcome. It is assumed that approximately 500 subjects will receive CP in the course of this study, extrapolating from the 250 known recipients to date. We would then have 500 exposed and 2,500 unexposed subjects assuming a 5:1 match. As of June 2020, nearly 4,000 COVID-19 patients have been admitted, making our sample viable. Current data shows an approximately 25% mortality rate, among those admitted who either have died or were discharged. Assuming independent observations, we would be able to detect a hazard ratio of 1.3 with 80% power and 1.35 with 90% power. Given the matched design, it is necessary to estimate a design effect due to the matching. A design effect of 2.0 would be considered extreme, assuming an intraclass correlation of 0.20 and cluster size of 6 [5:1]. This would result in an effective sample size of 1500 subjects. This would result in a detectable hazard ratio of 1.43 with 80% power and 1.50 with 90% power. These calculations assume alpha=0.05.

### **5.7 Withdrawal of Subjects**

We will not have contact with study subjects. We do not anticipate that Veterans will contact the study if they know that they received CP. If a study subject contacts the study and requests a withdrawal, we will not collect additional data from the subject. We will, however, continue to use data previously collected.

### **6.0 Reporting**

The Co-Chairs will be jointly responsible for ensuring that the study adheres to the reporting requirements of the VA Central IRB, local R&D Committee(s), and VA/VHA requirements (e.g., VHA Handbook 1200.12 and VHA Handbook 1058.01).

### **7.0 Privacy and Confidentiality**

All data will be stored in compliance with applicable VA policies. This study does not involve patient recruitment. All electronic databases related to the study will be stored on double-password protected servers behind the VA firewall. Once uploaded to networked data servers, the data are maintained in a separate network system dedicated to databases containing PHI or sensitive data. There are multiple levels of security to ensure the integrity and confidentiality of all data stored on the system. The desktop computers and the data servers require authentication for access and these computers and servers are assigned to authorized staff only.

Only personnel approved to be on the study by the R&D Committees will be allowed access to these files. Personnel that are removed from the study will have their access removed. To de-identify and protect PHI, scrambled social security numbers and dates will be used in the

intermediate databases. De-identified information is provided to the PIs by the study team inclusive of the Biostatistician, and database programmer. The final analytic database will not have any PHI and will include aggregated data only. Since the data used is aggregate, this cannot be used to uniquely identify any patient. A crosswalk document linking the study ID to the Patient ICN will be kept within a VINCI workspace. No outside sources can access these data.

Where applicable, we use encryption, physical security measures, restricted access, and locked file cabinets for paper records for data protection. VA study sites will utilize technologies that meet VA standards for data transfer to protect study data during transmission. For example, VA sensitive information will be transmitted using Federal Information Processing Standards (FIPS) 140-2 compliant encryption tools or Secure File Transfer Protocol (SFTP). In accordance with VA policy, incident reporting of theft, loss of data, loss of storage media, unauthorized access to sensitive data or storage media and non-compliance with security controls will be reported promptly to the study PIs, Privacy Officer and Information Security Officer.

Upon study completion, all research data will be maintained and/or destroyed, in accordance with the VHA Records Control Schedule (RCS 10-1) and VA Directive 6500. The study team will implement approved records dispositions, while ensuring that no records are destroyed without proper authorization. Decisions regarding disposal or disposition of the data, if necessitated, will be made with the approval of the appropriate oversight committees and VA regulations.

## **8.0 Communication Plan**

This is an analysis-only protocol involving 2 CSPEC programs, Boston and Seattle. The Chairs and Co-investigators communicate on a regular basis. For this analysis, due to the urgency, we will have weekly analyses to produce results of the associations of interest. As follow-up of Veterans continues for 1 year, we will continue to meet regularly to complete the objectives of the study.

The regulatory documents, including CIRB communications, will be maintained by Seattle and the protocol will be maintained by Boston. Seattle will also be monitoring serious adverse events related to study participation, which is limited to data security.

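### Do the planned weekly analyses, with no stated data cut or rule for repeated looks, inflate the study's false-positive rate?

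*Combined protocol and SAP*

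**What the plan says.** Section 8.0 (Communication Plan) states that "due to the urgency, we will have weekly analyses to produce results of the associations of interest". It continues: "As follow-up of Veterans continues for 1 year, we will continue to meet regularly to complete the objectives of the study". Neither sentence gives the number of weekly runs, a last run, or the status of a weekly result.

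Sample Size/Power, in section 5.6, expects that "approximately 500 subjects will receive CP in the course of this study, extrapolating from the 250 known recipients to date". It plans for "500 exposed and 2,500 unexposed subjects assuming a 5:1 match" and notes that "These calculations assume alpha=0.05". That is the only place where an error level appears.

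The Statistical Analysis Plan, also in section 5.6, uses the bootstrap "to calculate percentile-based confidence intervals (CI) for survival difference and hazard ratio estimates". It states no confidence level, data cut, last admission date or adjustment for repeated analysis.

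Other parts are firmer. Outcome variables names 30-day all-cause mortality as primary. The Abstract commits to inverse probability weighted pooled logistic models for the per-protocol analogue, and the Statistical Analysis Plan makes standardization a secondary method. Section 7.0 refers to a final analytic database, without a date.

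**The concern.** The weekly runs are effect analyses, not data checks, and the exposed group is expected to double while they go on. Testing accumulating data again and again at an unadjusted 0.05 raises the chance that at least one look crosses by luck. The study also wants early evidence (Abstract, section 2.2), and some groups in the plasma registry will contribute summary statistics to a collaboration. An early favourable week could therefore be taken up before the data are complete.

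If the plan let any week stand as the result, two things would be at stake. The error rate would exceed the 5% behind the power statement, and readers could not tell a planned result from the most favourable of many.

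**Working it through.** **Step 1: the plan's own figures.** Inputs from Sample Size/Power: 500 exposed, 2,500 unexposed, "approximately 25% mortality rate, among those admitted who either have died or were discharged", alpha 0.05. For a hazard ratio of 1.3, the exposed risk is 1 − 0.75^1.3 = 0.312, a difference of 0.062 from 0.25. The pooled risk is (0.312 + 5 × 0.25)/6 = 0.260. The standard error is √[0.260 × 0.740 × (1/500 + 1/2,500)] = 0.0215 under no effect, and √[0.312 × 0.688/500 + 0.25 × 0.75/2,500] = 0.0225 under the alternative. Power = Φ[(0.0620 − 1.96 × 0.0215)/0.0225] = Φ(0.885) = 81%.

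The same method gives 90.5% for 1.35. With the effective sample of 1,500 it gives 80.2% for 1.43 and 89.3% for 1.50. All agree with the stated 80% and 90%. (A two-sided Schoenfeld calculation on 750 events gives 76.4% for 1.3, so the two-proportion form is the one that fits.) The power statement therefore describes one two-sided test at 0.05. It says nothing about weekly looks.

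**Step 2: error if any week could count.** This rule is an assumption; it is not in the documents. Take no true effect, |z| > 1.96 at each look, information proportional to plasma recipients, and looks evenly spaced. The first look falls at 250/500 = 0.50 of final information.

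For two looks the correlation of the statistics is √0.50 = 0.707. The chance of any crossing is 0.05 + 0.05 − P(both) = 0.10 − 0.0169 = 8.3%. Numerical integration for more looks gives:

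| Looks, 50% to 100% information | Any crossing |
|---|---|
| 2 | 8.3% |
| 8 | 12.2% |
| 12 | 13.0% |
| 26 | 14.2% |
| 52 | 15.0% |

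An independent simulation (200,000 null paths) gave 8.4%, 12.3%, 13.0%, 14.4% and 15.1%.

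**Step 3: sensitivity to the first look.** The 250 are all recipients known at the time of writing. They are not patients who meet the section 5.1 criteria, were treated within 2 days and have 30 days of follow-up, so 50% is only one possible start. By simulation:

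| First look at | 2 looks | 52 looks |
|---|---|---|
| 10% | 9.5% | 26.0% |
| 25% | 9.1% | 20.5% |
| 50% | 8.4% | 15.1% |
| 75% | 7.4% | 10.8% |
| 90% | 6.5% | 8.2% |

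Fifty-two looks is itself an extreme. The one-year sentence concerns follow-up and meetings. Once the last patient has passed day 30, further weekly runs add no new primary-outcome time.

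**Step 4: would early signals fade?** Under the same rule, the share of runs with any crossing that are not significant at the last look is 1 − 0.05/P(any crossing).

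- From 50%: 1 − 0.05/0.0831 = 40% (2 looks); 1 − 0.05/0.1302 = 62% (12); 1 − 0.05/0.1418 = 65% (26).
- From 75%, 26 looks (10.4%): 1 − 0.05/0.1039 = 52%.
- From 90%, 26 looks (8.0%): 1 − 0.05/0.0802 = 38%.

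So it is not generally true that most early signals vanish.

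**Step 5: one analysis carries the conclusion.** Looking on other weeks then leaves that analysis's nominal level at 5%, however many runs there are.

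**Step 6: price of a formal boundary.** A constant boundary that holds 5% from a 50% start is z = 2.359 for 8 looks and 2.458 for 52. Matching intervals would be wider by 2.359/1.96 = 1.20 to 2.458/1.96 = 1.25 times, to guard against a claim rule the plan does not make.

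**The case for a change.** The best case for a change is that the omission is real and cheap to mend. No section fixes a data cut, a final run or a confidence level. The plan invokes alpha 0.05, the study exists to give early signals, and estimates may go into a pooled analysis. A few sentences naming one reporting analysis and labelling weekly estimates descriptive would cost nothing, and no alpha control need be imposed. Early runs would also include patients without 30 days of follow-up.

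The textual part stands: those items are absent, and stating them would help a reader. The rest is weaker. Alpha appears only in the power paragraph, and the analysis section plans estimates and intervals without a decision. Weekly results cannot stop accrual or alter treatment, because the study only collects existing records. The planned size, the final analytic database and the reference to completing the objectives all point to a last analysis, though none dates it. Kaplan-Meier and pooled logistic methods, which the plan names, can take patients with incomplete follow-up as censored. What remains is a reporting policy.

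**Conclusion.** No change is called for. The plan leaves open when the reported analysis is run and at what confidence level. It does not leave open the primary outcome, and the main estimator can be read from the Abstract together with the secondary label on standardization.

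The error rates of 8% to 15% (50% start), or 6.5% to 26% over all the starts examined, belong to an any-week-counts rule that appears nowhere in the documents. They also rest on an assumed number of looks, an assumed first look, and information proportional to recipients.

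With one analysis carrying the conclusion, the multiplicity cost is zero and the level is the nominal 5%. That 5% also presumes no residual confounding and valid bootstrap intervals, which no rule on looks would secure. Competent analysts would be expected to report 95% intervals on a stated data cut with complete 30-day follow-up and to treat the weekly runs as provisional. A sequential boundary would widen intervals by about 20% to 25% and control nothing the plan puts at risk. The judgement would differ if an early weekly result were meant to support a claim of effect.
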